13.2. Case Report Form completion

The electronic CRFs will include (but will NOT be limited to) the following Forms (see **Table 7: Case Report Forms in IIH-Advance**).

Table 7: Case Report Forms in IIH-Advance

Form Name	Schedule for submission
ICF and Screening CRF	At the point of the consent / screening visit
Randomisation CRF	At the point of randomisation
Baseline and follow up CRFs including participant reported outcome measures	As soon as possible after each follow up assessment time point
Serious Adverse Event CRF	If expedited: submitted within 24 hours of research team becoming aware of event If non-expedited: submitted within 2 weeks of research team becoming aware of event
Change of status CRF	As soon as possible after the point of reduced participation or death

In IIH-Advance electronic CRFs will be used, and the relevant forms should be completed for each individual participant. All electronic CRFs must be completed on the EDC and thereby submitted to the Trial Office by the Trial Researchers (as delegated on the Trial Delegation Log) within the timeframes above.

In all cases, it remains the responsibility of the CI to ensure that the electronic CRFs have been completed correctly and that the data are accurate. This will be evidenced by the signature of the CI or delegate. The Trial Delegation Log will identify all those personnel with responsibilities for data collection.

The delegated staff completing the electronic CRFs should ensure the accuracy, completeness and timeliness of the data reported. This will be evidenced by validating and dating the electronic CRF.

Where the CRF is not the source data, data reported on each electronic CRF will be consistent with the source data and any discrepancies will be explained. All missing and ambiguous data will be queried. Staff delegated to complete CRFs will be trained to adhere to IIH-Advance working instructions.

The following guidance applies to data and partial data:

- Time format – all times should be in accordance with the 24hr clock
- Rounding conventions – rounding should be to the nearest whole number: If the number you are rounding is followed by 5, 6, 7, 8, or 9, round the number up. Example: 3.8 rounded to the nearest whole number is 4. If the number you are rounding is followed by 1, 2, 3 or 4, round the number down. Example: 3.4 rounded to the nearest whole number is 3
- Trial-specific interpretation of data fields – where guidance is needed additional information will be supplied
- Entry requirements for concomitant medications (generic or brand names) – generic names should be used where possible
- Missing/incomplete data – should be clearly indicated – all blank fields will be queried by the Trial Office
- Protocol and GCP non-compliances should be reported to the Trial Office on discovery.

13.3. Participant reported questionnaires

Participant reported outcome measures will be completed by the Trial Researcher entering the participant reported data directly into the EDC during the remote interview.

13.4. Actigraphy data

Actigraphy data from a wearable device, provided for the trial, will be collected and the device sent to the Trial Office. A member of the Trial Office will download the data and store it securely on a UoB server.

13.5. OCT Scans

OCT scans are performed by Specsavers. Copies of the OCT scans will be stored by Specsavers as per usual Specsavers processes. Participants will be made aware of this in the PIS and asked to acknowledge it on the ICF.

13.6. Data management

Processes will be employed to facilitate the accuracy and completeness of the data included in the final report. These processes will be detailed in the trial specific Data Management Plan and include the processes of data entry, data queries and self-evident corrections on trial data.

Data entry will be completed by the trial researchers via a bespoke BCTU EDC. This system will conduct automatic range checks for specific data values to ensure high levels of data quality. Queries will be raised using data clarification forms (DCFs) via the trial database, with the expectation that these queries will be completed by the researchers within 30 days of receipt. Overdue data entry and data queries will be requested monthly.

13.7. Data security

UoB has policies in place, which are designed to protect the security, accuracy, integrity and confidentiality of Personal Data. The trial will be registered with the Data Protection Officer at UoB and will hold data in accordance with the Data Protection Act (2018 and subsequent amendments). The Trial Office has arrangements in place for the secure storage and processing of the trial data which comply with UoB policies.

The trial EDC incorporates the following security countermeasures:

Physical security measures: restricted access to the building, supervised onsite repairs and storages of back-up tapes/disks are stored in a fire-proof safe.

Logical measures for access control and privilege management: including restricted accessibility, access-controlled servers, separate controls of non-identifiable data.

Network security measures: including site firewalls, antivirus software and separate secure network protected hosting.

System management: the system will be developed by the Programming Team at the Trial Office and will be implemented and maintained by the Programming Team.

System design: the system will comprise of a database and a data entry application with firewalls, restricted access, encryption and role-based security controls.

Operational processes: the data will be processed and stored within BCTU.

System audit: The system will benefit from the following internal/external audit arrangements:

- Internal audit of the system
- Periodic IT risk assessment

Data Protection Registration: UoB's Data Protection Registration number is Z6195856.

13.8. Archiving

The TMF will be stored at BCTU for at least 3 years after the end of the trial. Long-term offsite data archiving facilities will be considered for storage after this time; data will be stored securely and confidentially for at least 10 years. BCTU has standard processes for both hard copy and digital archiving. No documents should be destroyed without prior approval from the BCTU Director or their delegate.

14. Quality Control and Quality Assurance

14.1. Site set-up and initiation

IIH-Advance will be a centralised trial. University of Birmingham will be the sole site. The IIH-Advance team will be split into the Trial Office, responsible for trial management and coordination, and the Trial Researchers, responsible for participant contact, follow up, and safety. Trial Doctors will be a medically qualified subset of Trial Researcher.

All Trial Researchers are required to sign the Trial Delegation Log, which details which participant-facing and trial delivery tasks have been delegated to them by the CI. The Trial Delegation Log should be kept up to date by the CI. It is the CI's responsibility to inform the Trial Office of any changes in the Trial Researcher team.

Prior to commencing recruitment, the Trial Researcher team will undergo a process of site initiation, either a meeting or a video call, covering aspects of the trial design, protocol procedures, adverse event reporting, collection and reporting of data and record keeping. All Trial Researchers will be trained by the CI and Trial Office in trial procedures before any participant contact.

Compliance standards with regards to data transfer and participant contact will be described in the UoB-Specsavers contract.

14.2. Monitoring

The central monitoring requirements for this trial have been developed in conjunction with the trial specific risk assessment and are documented in the trial specific monitoring plan.

14.2.1. Central monitoring

The Trial Office will check entered ICFs and CRFs for compliance with the protocol, data consistency, missing data and timing at a frequency and intensity determined by the Data Management Plan. Trial researchers will be sent DCFs requesting missing data or clarification of inconsistencies or discrepancies as per the Data Management Plan. Any such monitoring activities will be reported to the TMG and any issues noted will be followed up to resolution.

14.3. Notification of Serious Breaches

The sponsor is responsible for notifying the REC of any serious breach of the conditions and principles of GCP in connection with that trial or of the protocol relating to that trial. Trial Researchers must therefore notify the Trial Office of any suspected trial-related serious breach of Good Clinical Practice (GCP) and/or the trial protocol as soon as they become aware of them. Where the Trial Office is investigating whether a serious breach has occurred, Trial Researchers must co-operate with the Trial Office in providing sufficient information to report the breach to the REC where required and in undertaking any corrective and/or preventive action.

15. End of Trial Definition

The end of trial will be the date of the last data capture including sample analysis and DCF resolution. This will allow time for the completion of protocol procedures, data collection, data input and data cleaning.

The Trial Office will notify the REC and Sponsor within 90 days of the end of trial. Where the trial has terminated early, the Trial Office will notify the REC within 15 days of the end of trial. The Trial Office will provide the REC and Sponsor with a summary of the clinical trial report within 12 months of the end of trial.

16. Statistical Considerations

16.1. Sample size

Examination of various IIH datasets held (including the IIH:WT trial²⁵, the IIH:Life cohort, and our previously published clinical trials in IIH²⁶) suggest it is anticipated that in the population of patients who receive standard of care only 5% will have resolution of papilloedema (100% reduction in the excess elevation of the optic nerve swelling). Further analysis of these datasets revealed that in those who achieved at least a 12% reduction in body weight, between 30 and 50% had a complete resolution of papilloedema. For the purposes of the sample size calculation, we have taken a conservative estimate of 37% (the median estimate).

With a type I error of 0.05, a type II error of 0.1 (corresponding to a power of 90%), a responder rate in the control arm of 5% and responder rate of 37% in the Tirzepatide arm, a sample size of 32 participants per arm is required. Inflating this to account for 25% attrition (for missing data and withdrawal) would require 43 patients per arm (86 overall).

After 50% of the planned sample size has been recruited and treated (i.e. at the end of the first randomisation R1), an assessment of the missing data is planned to ensure the levels observed fall below that assumed during this calculation, with the option to increase the sample size based on this if needed. This trial has been powered to answer the primary question for R1 only. The subsequent questions remain unpowered. This remains a limitation, however powering for these questions would result in a trial sample size that was infeasible. The purpose of these questions is to provide some high-quality evidence.

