1.6.3. Justification for choice of intervention

Weight loss is the only proven condition modifying treatment^{25,26}. We are choosing to induce weight loss through treatment by Tirzepatide, chosen over other GLP-1R agonists as it has a suggested greater efficacy compared to Semaglutide⁴¹. In the original paper regarding the efficacy of Tirzepatide, the mean reduction in body weight of patients who received Tirzepatide was 14% at six months⁴². It is anticipated that the patients who receive active treatment as part of IIH-Advance will experience a similar weight loss. Given the patient population recruited to IIH-Advance is similar to the population who were recruited to IIH:WT²⁵(which itself is more similar to the Wilding *et al.* population⁵⁹ where a larger reduction in body weight was seen), we assume an anticipated 14% body weight loss in the active arm of IIH-Advance.

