16.2. Analysis of outcomes

A separate Statistical Analysis Plan will be produced and will provide a more comprehensive description of the planned statistical analyses. A brief outline of the planned analyses is given below.

Unless reported otherwise, the threshold for determining statistical significance from hypothesis testing will be represented by a p-value of <0.05. Where parametric tests have been specified dependent on the normality of data distribution, this will be assessed using appropriate graphics (for example histograms and q-q plots) prior to application of the test. Where randomisation is minimised by stratification variables, the main estimators will be adjusted for such variables for the primary outcome at stage R1.

Data pertaining to outcome measures will be transformed as per user manuals and standard practice to derive clinically meaningful indices where relevant.

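### The 37% response rate behind the stated 90% power comes from people who lost at least 12% of body weight but is applied to everyone randomised to Tirzepatide, so the power claim is not supported

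*Protocol*

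**What the plan says.** All of the sample size reasoning is in Protocol section 16.1.

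- Control rate: the sponsor's datasets suggest that "in the population of patients who receive standard of care only 5% will have resolution of papilloedema". This describes standard-of-care patients in general, with no condition on weight change.
- Tirzepatide rate: the same datasets showed that "in those who achieved at least a 12% reduction in body weight, between 30 and 50% had a complete resolution of papilloedema". From this, "we have taken a conservative estimate of 37% (the median estimate" is the sponsor's description of the value chosen.
- Calculation: the inputs become "a responder rate in the control arm of 5% and responder rate of 37% in the Tirzepatide arm", with a type I error of 0.05 and 90% power. The result is 32 per arm, raised to 43 per arm (86 overall) for 25% attrition.

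Two other sections bear on this. Section 1.6.3 gives the expected weight loss: "we assume an anticipated 14% body weight loss in the active arm of IIH-Advance". That figure is carried over from the mean loss at six months in an earlier Tirzepatide trial. Section 16.2.1 takes as denominator all participants in the arm and counts a missing primary outcome as a failure, unless data from an unscheduled visit can be used.

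**The concern.** The 37% is conditional on something that happens after randomisation, namely losing at least 12% of body weight. Section 16.1 then uses it for everyone allocated to Tirzepatide, whether or not they lose that much. The control rate is not restricted in the same way, and the primary analysis does not select on weight loss. The two sides of the planned comparison therefore describe different kinds of population, and only one of them matches the analysis.

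This is the only question the trial is powered for, and it sets the target of 86. The check planned at half recruitment looks at missing data only, so a Tirzepatide response rate below the planned one would not be picked up there. A null or borderline result would be read against a 90% power claim that the protocol's own premises do not establish.

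**Working it through.** **Inputs from the Protocol.** Control rate 5%; Tirzepatide rate 37%; range 30–50% among those losing at least 12%; type I error 0.05; power 90%; attrition 25% (all 16.1). Allocation 1:1 (3.1.1). Mean loss 14% (1.6.3). All participants in the denominator, missing as failure (16.2.1). Section 16.1 does not state sidedness; two-sided is assumed.

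**Inputs not in the documents.** The share *q* of the Tirzepatide arm losing at least 12%, and the response rate *r* in the rest. Both are varied below.

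**Step 1: reproduce the plan's figure.** For two proportions, with p̄ = (0.05 + 0.37)/2 = 0.21:

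n = [1.96·√(2·p̄(1−p̄)) + 1.2816·√(p₁(1−p₁) + p₂(1−p₂))]² / (p₂−p₁)²

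= [1.96·√0.3318 + 1.2816·√(0.0475 + 0.2331)]² / 0.32² = 31.9, so 32 per arm.

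32/0.75 = 42.7, so 43 per arm and 86 overall. Power at 32 per arm is 90.1%. The plan's numbers reproduce.

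**Step 2: whole-arm rate.** p_T = q × 0.37 + (1−q) × r. Take r = 5%, the protocol's own rate without Tirzepatide. Power uses the same formula solved for power, at 32 per arm:

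| Share reaching 12% (q) | Whole-arm rate | Power |
|---|---|---|
| 100% | 37.0% | 90% |
| 96% | 35.7% | 88% |
| 90% | 33.8% | 85% |
| 83% | 31.6% | 80% |
| 70% | 27.4% | 69% |

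For example, at q = 70%: 0.70 × 0.37 + 0.30 × 0.05 = 0.274. With a more generous r = 20%, q = 70% gives 0.319 and power of 81%.

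**Step 3: what a mean of 14% implies for q.** The documents give no standard deviation. If weight loss were normal with mean 14, then q = Φ(2/SD). An SD of 4 to 10 percentage points, which is an assumption, gives q of 69% to 58%. For q to be 96%, the SD would have to be about 1.1 points.

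**Step 4: vary the conditional rate over the protocol's own range.** With r = 5% and 32 per arm:

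| Rate among those losing ≥12% | Power, q = 100% | Power, q = 70% |
|---|---|---|
| 30% | 76% | 53% |
| 37% | 90% | 69% |
| 40% | 94% | 75% |
| 50% | 99% | 89% |

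**Step 5: apply the analysis rule in 16.2.1.** With 43 per arm and 25% missing in each arm counted as failures, every rate is multiplied by 0.75, so 5% becomes 3.75%:

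| Underlying Tirzepatide rate | Analysed rate | Power, 43 per arm |
|---|---|---|
| 37% | 27.75% | 88% |
| 30% | 22.5% | 74% |
| 25% | 18.75% | 60% |

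**The case against.** The sample size arithmetic is correct; what is in dispute is a planning assumption. That stands.

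The protocol does link the two weight figures: the anticipated mean of 14% lies above the 12% threshold. Section 1.6.3 also likens the trial population to one in which a larger loss was seen, so 14% may be a cautious mean. This is fair, and a higher mean would raise the share reaching 12%. It does not close the gap, because a mean two points above a threshold does not put everyone above it. Sections 7.1 and 7.3 allow titration to differ between participants, which is a further source of spread.

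A reader might infer that the whole-arm rate must be below 37% and that 90% power is certainly not delivered. The documents do not support that. It would follow only if response among those reaching 12% were exactly 37% and the others responded less often. The protocol gives 30–50% for the first group. At 50%, power is still 89% with 70% of the arm reaching 12%, and above 90% with somewhat more. Nor do the documents establish that a large minority will fall short of 12%: that rests on an assumed spread.

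On the word conservative, 37% is below the 40% midpoint of the range, so the sponsor did not pick a high value. But it is described as the median estimate, the range starts at 30%, and it holds no allowance for people who do not reach 12%.

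**Conclusion.** The concern holds as one about an unsupported input. The 37% describes a subset defined by achieved weight loss, it is used for the whole arm, and nothing elsewhere in the protocol discounts it. The 90% claim needs either nearly every Tirzepatide participant to lose at least 12%, or a response above 37% among those who do. The protocol argues for neither.

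The direction, at a conditional rate of 37%, requires only that people losing less respond less often. That is the trial's own premise; section 1.3 reports that greater weight loss went with greater reduction in intracranial pressure. The size cannot be fixed from the documents. With 70% of the arm reaching 12%, an illustrative share, and 5% response in the rest, power runs from about 53% to 89% across the stated 30–50% range. Separately, even an underlying 37% in the whole arm gives about 88% once 25% missing in each arm are counted as failures.

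The primary outcome, the analysis and the type I error are unaffected. What needs correcting is the justification of the sample size and the power quoted for it.

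**What to change.** In section 16.1:

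1. State that 37% is the rate among people losing at least 12% of body weight, and drop the word conservative.
2. State the assumed share of the Tirzepatide arm reaching 12% and the assumed response rate in the rest, with their source, and derive the whole-arm rate from them.
3. Restate power for 86 randomised participants as a short table over plausible whole-arm rates, computed on 43 per arm with missing outcomes as failures, to match 16.2.1. With 25% missing in each arm, underlying rates of 37%, 30% and 25% against 5% give about 88%, 74% and 60%. A table based on 32 evaluable per arm would not match the planned analysis.

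The cost is a change of wording in the protocol, carried into the SAP if it repeats the calculation. No extra participants are needed to correct the statement. The downside is a less favourable stated power; whether to enlarge the trial in response is a separate decision for the sponsor.

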16.2.1. Primary outcome

Resolution of papilloedema at the 6 month assessment. Where patients are missing the primary outcome (for example due to non-attendance at 6-month visit), they shall be treated as a failure and included in the denominator only (unless there is data from an unscheduled visits which could be utilised).

Resolution of papilloedema will be reported as n/N where n is the number of participants with resolution of papilloedema and N the total number of participants in the corresponding trial arm, and percentages as appropriate. Logistic regression model will be used to analyse the primary outcome. Risk ratio, risk difference and the associated 95% confidence intervals will then be derived using marginal standardisation method.

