16.2.4. Missing data and sensitivity analyses

For the primary outcome, where patients are missing the primary outcome (for example due to non-attendance at 6-month visit), they shall be treated as a failure and included in the denominator only and thus no imputation of missing data is planned.

An analogous strategy for binary secondary outcomes will be used.

For continuous, or pseudo-continuous secondary outcomes with only one post baseline time-point of collection, no imputation will be performed and the number of participants missing the relevant outcome data reported.

For continuous, or pseudo-continuous secondary outcomes with more than one post-baseline time-point of collection, the above-described modelling approach will implicitly impute observations using patient-within-arm imputations methods suitable for longitudinal data imputation.

Full details will be included in the Statistical Analysis Plan.

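### Section 16.1 inflates for 25% attrition as if missing participants left the analysis, but the primary analysis counts them as failures: formula power is about 88%, not 90%, and the 25% missing-data check is set too high

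*Protocol*

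**What the plan says.** Section 16.1 fixes the planning rates as "a responder rate in the control arm of 5% and responder rate of 37% in the Tirzepatide arm", with a type I error of 0.05 and 90% power, and obtains 32 per arm. It then allows for losses: "Inflating this to account for 25% attrition (for missing data and withdrawal) would require 43 patients per arm (86 overall").

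Section 16.2.1 sets the rule for participants without a 6-month primary outcome: "they shall be treated as a failure and included in the denominator only". The one exception is where an unscheduled visit supplies usable data. The same section defines the denominator as everyone in the arm. Section 16.2.4 repeats the rule, without that exception: "included in the denominator only and thus no imputation of missing data is planned".

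Section 16.1 also plans a look at missing data once half the sample has been recruited and has completed stage R1. Its purpose is to confirm that missingness is below the level assumed, "with the option to increase the sample size based on this if needed". No formula for an increase is given.

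**The concern.** Dividing by one minus the attrition rate is the right inflation when participants with missing outcomes leave the analysis: 43 are randomised, about 32 are analysed, and the rates among those 32 are still 5% and 37%. Under the protocol's own rule nobody leaves. All 43 are analysed, and each missing outcome counts as a non-response, so both rates shrink in proportion to the missingness and the difference between them shrinks too. The larger denominator does not fully make up for the smaller difference.

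Three things are affected. The stated power does not belong to the stated analysis. The planned risk difference, which section 16.2.1 lists among the estimates to be reported, is overstated. And the mid-trial check takes its threshold from the same calculation, so it could pass a level of missingness at which the trial is already below its power target by the protocol's own method.

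**Working it through.** **Inputs** (Protocol 16.1 unless stated): control rate p1 = 0.05; tirzepatide rate p2 = 0.37; alpha = 0.05, taken as two-sided because that reproduces the protocol's figure; power 90%; attrition d = 0.25; 1:1 allocation (3.1.1); missing counted as failure (16.2.1, 16.2.4). Assumptions: equal missingness in the two arms, no missing outcome rescued by an unscheduled visit, and planning rates that apply to participants whose outcome is observed.

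**Step 1: reproduce the protocol.** Pooled-variance formula without continuity correction, with p̄ the mean of the two rates:

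n = [1.96·√(2p̄(1−p̄)) + 1.2816·√(p1(1−p1) + p2(1−p2))]² / (p2−p1)²

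With p̄ = 0.21: n = [1.96×0.5760 + 1.2816×0.5297]² / 0.32² = 31.9, so 32. Power at 32 is 90.1%. Then 32/0.75 = 42.7, so 43 per arm and 86 overall. All the stated figures are reproduced.

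**Step 2: apply the analysis rule.** Multiply both rates by 0.75:
- control 0.05×0.75 = 3.75%
- tirzepatide 0.37×0.75 = 27.75%
- risk difference 24.0 points, against 32

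**Step 3: power at 43 per arm, same formula.** Here p̄ = 0.1575.

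z = [0.24×√43 − 1.96×0.5152] / 0.4864 = (1.5738 − 1.0097)/0.4864 = 1.16, so power = 87.7%.

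For 90% the formula gives n = 46.3, so 47 per arm (94 overall).

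**Step 4: exact power by enumeration.**

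| Test | 32 per arm, 5% vs 37% | 43 per arm, 3.75% vs 27.75% |
|---|---|---|
| Chi-squared, uncorrected | 92.8% | 92.0% |
| Fisher | 87.0% | 85.4% |

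The direction is the same for both tests, with a drop of about 1 to 2 points.

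**Step 5: the mid-trial threshold.** Formula power at 43 per arm when the missing count as failures:

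| Missing | Power | n per arm for 90% |
|---|---|---|
| 15% | 92.3% | 40 |
| 20% | 90.2% | 43 |
| 21% | 89.7% | 44 |
| 25% | 87.7% | 47 |
| 30% | 84.8% | 51 |
| 35% | 81.4% | 56 |

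The 90% target is held up to about 20% missing, not 25%.

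**Step 6: unequal missingness, as an illustration.** With 25% missing overall but 30% on tirzepatide and 20% on control, formula power at 43 per arm is 82.5%. The reverse split gives 91.7%.

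**The case against.** The strongest reply is that the shortfall is partly a product of the approximation. Exact chi-squared power stays above 90% after dilution, and an unadjusted likelihood-ratio test, the nearest simple equivalent to the planned logistic regression that can be enumerated, behaves the same way (about 93% before, 92% after). Fisher's test falls short of 90%, but it is not planned and is short before any dilution. This stands, and it is why the point is modest. It does not remove the mismatch: the protocol claims 90% by one formula, and that formula gives 88% for the analysis it specifies. The change in the planned risk difference from 32 to 24 points does not depend on the choice of test.

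It is also fair that 25% is a planning allowance. Unscheduled OCT data may be used (16.2.1), and participants who stop treatment can remain in follow-up (section 11). Both would lower missingness, and at 20% the formula still gives 90.2%.

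Two stronger readings are tempting and are not supported. A reader might infer that the protocol's re-estimation rule under-corrects. No such rule is written: the protocol gives a level to compare against and an option to increase. Only if 32/(1 − missing) were reused would the increase fall short, for example 50 per arm at 35% missing, with 86.9% power where 56 are needed. A reader might also infer that no sensitivity analysis for missing primary outcomes will be done. Section 16.2.4 defers full details to the statistical analysis plan, which is not shown, so its absence from the protocol is no finding.

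**Conclusion.** The point holds as an inconsistency between the sample size and the primary analysis. It is not an arithmetic slip, since 32, 43 and 86 all reproduce, and counting missing outcomes as failures is a legitimate choice. The sample size was simply not calculated for that choice. With 25% missing equally in both arms and no rescue from unscheduled visits, the design has about 88% power by the protocol's formula instead of 90%, and a planned risk difference of 24 points instead of 32. A threshold of 25% missing would let 21% to 25% pass with formula power already below 90%. The loss is small, about 2 points by formula and about 1 to 2 points by exact calculation. It would be larger with more missing data or with more loss on tirzepatide than on control, and smaller or absent in the opposite cases.

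**What to change.** In section 16.1, state the rates the analysis will see: 3.75% against 27.75% with 25% missing, a risk difference of 24 points, 43 per arm, and about 88% power by the formula used. If the sponsor prefers to keep 90% by that formula, it requires 47 per arm (94 overall).

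Base the mid-trial check on the same diluted rates. Either set the trigger at about 20% missing, or recalculate power at the observed missingness and act on that. Say that any increase will be computed from the diluted rates and not from 32/(1 − missing).

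Keeping 86 participants, the change is one of wording. Its only cost is that the stated power falls by about 2 points. The missing-as-failure rule and the conduct of the trial stay as they are.
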